5.4 Removal of Subjects from Therapy or Assessment

5.4.1 Discontinuation of Individual Subjects

Each subject has the right to withdraw from treatment or the study at any time. In addition, the investigator may discontinue a subject from treatment or the study at any time if the investigator considers it necessary for any reason, including the occurrence of an adverse event or noncompliance with the protocol.

If, during the course of study drug administration, the subject prematurely discontinues treatment, the procedures outlined for the applicable Premature D/C Visit should be completed as defined in [Table 4](#). It is recommended that this visit occur on the day of study drug discontinuation; however, this visit should occur within 2 days following their final dose of study drugs and prior to the initiation of any other anti-HCV therapy. However, these procedures should not interfere with the initiation of any new treatments or therapeutic modalities that the investigator feels are necessary to treat the subject's conditions. Following discontinuation of study drugs, the subject will be treated in accordance with the investigator's best clinical judgment. The date of the last dose of study drug and reason for discontinuation will be recorded in the eCRF. The subject should then begin the PT Period where the subject will be monitored for 48 weeks for safety, HCV RNA, the emergence and persistence of resistant viral variants, and assessments of PROs.

If a subject discontinues from the PT Period, the subject should return for post-treatment discontinuation procedures defined in [Table 5](#). The reason for discontinuation will also be recorded in the eCRF.

If a subject is discontinued from study drug (Treatment Period) or the PT Period with an ongoing adverse event or an unresolved laboratory result that is significantly outside the reference range, the investigator will attempt to provide follow-up until a satisfactory clinical resolution of the laboratory result or adverse event is achieved (Section [6.7](#)).

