5.4.1.1 Virologic Failure Criteria for Subject Management

The following criteria will be considered evidence of virologic failure leading to discontinuation of study drug while receiving study drug and will be discontinued from study drug:

- Confirmed increase from nadir in HCV RNA (defined as 2 consecutive HCV RNA measurements of $> 1 \log_{10}$ IU/mL above nadir) at any time point during treatment; or
- Failure to achieve HCV RNA $<$ LLOQ by Week 8; or
- Confirmed HCV RNA \geq LLOQ (defined as 2 consecutive HCV RNA measurements \geq LLOQ) at any point during treatment after HCV RNA \leq LLOQ.

Confirmatory testing should be completed as soon as possible. Subjects should remain on study drug treatment until the virologic failure has been confirmed. If any of the above criteria are met, the subject will discontinue study drug treatment (Section [5.4.1](#)).

Subjects with HCV RNA < LLOQ at the end of treatment and who have a confirmed HCV RNA \geq LLOQ (defined as 2 consecutive HCV RNA measurements \geq LLOQ) at any point in the PT Period will be considered to have relapsed. Confirmation of an HCV RNA \geq LLOQ in the PT Period should be completed as soon as possible per Section [5.1.3](#).

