6.3 Missing Data Imputation

No data will be imputed for any efficacy or safety analyses except for analyses of the HCV RNA endpoints.

HCV RNA values will be selected for the SVR₁₂ analysis based on defined visit windows. When there is no HCV RNA value in a visit window based on defined visit windows, the closest values before and after the window, regardless of the value chosen for the subsequent and preceding window, will be used for the flanking imputation described below.

If a subject has a missing HCV RNA value at a post-Day 1 visit, but with undetectable or unquantifiable HCV RNA levels at both the preceding value and succeeding value, the HCV RNA level will be considered undetectable or unquantifiable, respectively, at this visit for this subject. For SVR₁₂ analysis, if there is no value in the appropriate window

after flanking imputation but there is an HCV RNA value after the window, then it will be imputed into the SVR₁₂ window. Similarly, for SVR₂₄ analysis, if there is no value in the appropriate window after flanking imputation but there is HCV RNA value after the window, then it will be imputed into the SVR₂₄ window.

If a subject starts another treatment for HCV, then all HCV RNA and PRO values for this subject measured on or after the start date of the new HCV treatment will be excluded from analyses. The subject will be considered a failure for summaries of viral response at all time points after the start of the new HCV treatment.

HCV RNA < LLOQ Analyses for SVR

If a subject is missing an HCV RNA value for the visit window associated with the analysis of SVR after performing the imputations described above, then this value will be imputed with an HCV RNA value from a local laboratory if present; otherwise, the HCV RNA value for this visit will be missing. Subjects with missing HCV RNA data in the analysis window, after imputations, will be imputed as a failure.

HCV RNA Analyses for Relapse and Virologic Failure

If HCV RNA values from the central laboratory are missing but a local laboratory value is present in the appropriate time period, then the local laboratory value will be used to assess post-treatment relapse and on-treatment virologic failure.

Missing Data Imputation for PRO Questionnaires

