10.0 Efficacy Analysis

10.1 General Considerations

Analyses will be performed on the intent-to-treat (ITT) population. Sensitivity analyses of the primary endpoint, when applicable, will be performed on the mITT-GT-VF population specified in Section 5.1.1.

Missing data will be imputed as described in Section 6.3 for analyses of the HCV RNA endpoints of SVR.

Plasma HCV RNA levels will be determined for each sample collected by the central laboratory using the Roche COBAS TaqMan® real-time reverse transcriptase-PCR (RT-

PCR) assay v.2.0. For this assay, the lower limit of quantitation (LLOQ) is 25 IU/mL regardless of genotype, and the lower limit of detection (LLOD) varies by genotype. For GT3, the lower limit of detection (LLOD) is 20 IU/mL; for GT2, LLOD is 20 IU/mL. HCV RNA results that are detectable but not quantifiable are reported as "< 25 IU/mL HCV RNA detected" and those that are undetectable are reported as "HCV RNA not detected" in the database.

The notation "HCV RNA < LLOQ" is used to represent all HCV RNA values < 25 IU/mL, including values reported as "HCV RNA not detected" or "< 25 IU/mL HCV RNA detected." HCV RNA \geq LLOQ are all quantifiable values of 25 IU/mL or greater.

IL28B rs12979860 will be resulted as C/C, C/T, or T/T by the central laboratory.

Definitions for Efficacy Endpoints

Note that a confirmed quantifiable post-treatment value is defined as two consecutive post-treatment HCV RNA measurements \geq LLOQ. During treatment, a confirmed quantifiable value is defined as any two consecutive HCV RNA values \geq LLOQ, either both during treatment or at the final treatment measurement and the next consecutive post-treatment measurement.

Breakthrough = confirmed HCV RNA \geq LLOQ after HCV RNA < LLOQ during treatment, or confirmed increase from nadir in HCV RNA (two consecutive HCV RNA measurements $> 1 \log_{10}$ IU/mL above nadir) at any time point during treatment. A single breakthrough value (\geq LLOQ or $> 1 \log_{10}$ IU/mL above nadir) followed by lost to follow-up will be considered a breakthrough (i.e., will not require confirmation).

On-treatment virologic failure = breakthrough or failure to suppress during treatment (all on-treatment values of HCV RNA \geq LLOQ) with at least 6 weeks (defined as study drug duration \geq 36 days) of treatment for 12-week and 8-week treatment or at least 26 days of treatment for 6-week treatment.

RVR (rapid virologic response) = HCV RNA < LLOQ in the Week 4 window.

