EOTR (end of treatment response) = HCV RNA < LLOQ in the Week 12 window for 12-week regimen, Week 8 window for 8-week regimen, and Week 6 for 6-week regimen.

SVR₄ = HCV RNA < LLOQ in the SVR₄ window (4 weeks after the last actual dose of study drug) without any confirmed quantifiable (\geq LLOQ) post-treatment value before or during that SVR window.

SVR₁₂ = HCV RNA < LLOQ in the SVR₁₂ window (12 weeks after the last actual dose of study drug) without any confirmed quantifiable (\geq LLOQ) post-treatment value before or during that SVR window.

SVR₂₄ = HCV RNA < LLOQ in the SVR₂₄ window (24 weeks after the last actual dose of study drug) without any confirmed quantifiable (\geq LLOQ) post-treatment value before or during that SVR window.

Relapse₁₂ = confirmed HCV RNA \geq LLOQ between end of treatment and 12 weeks after last actual dose of active study drug (up to and including the SVR₁₂ assessment time point) for a subject with HCV RNA < LLOQ at Final Treatment Visit who completes treatment, excluding re-infection as described below.

Relapse₂₄ = confirmed HCV RNA \geq LLOQ during SVR₂₄ window among subjects who achieved SVR₁₂ and have data available during the SVR₂₄ window, excluding re-infection.

Relapse_{late} = confirmed HCV RNA \geq LLOQ at any time after the SVR₂₄ assessment time point for a subject who achieved SVR₂₄ and has post-SVR₂₄ HCV RNA data available, excluding re-infection.

Relapse_{overall} = confirmed HCV RNA \geq LLOQ between end of treatment and up to and including the last HCV RNA measurement collected in the PT Period for a subject with HCV RNA < LLOQ at Final Treatment Visit who completes treatment. Completion of treatment is defined as a study drug duration \geq 37 days, \geq 49 days and \geq 77 days for planned treatment duration of 6 week, 8 weeks and 12 week, respectively. Also, include a

summary of Relapse_{overall} for subjects who prematurely discontinued treatment, excluding re-infection.

For relapse analyses, the completion of treatment is defined as above. If the last available post-treatment value is \geq LLOQ, then the subject will be considered a relapse (i.e., will not require confirmation). Relapse analyses will exclude subjects who do not have any post-treatment HCV RNA values.

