HCV re-infection is defined as confirmed HCV RNA \geq LLOQ after the end of treatment in a subject who had HCV RNA $<$ LLOQ at Final Treatment Visit, along with the post-treatment detection of a different HCV genotype, subtype, or clade compared with baseline, as determined by phylogenetic analysis of the NS3 or NS5A, and/or NS5B gene sequences. Re-infection in the case of the same HCV subtype is defined as a clade switch, as indicated by the lack of clustering between the baseline and post-treatment sequences by phylogenetic analysis. If phylogenetic analysis is not possible due to technical difficulties, HCV re-infection may be determined with a confirmed HCV genotype or subgenotype switch by the Versant HCV Genotype Inno-LiPA Assay v2.0 or Sanger assay.

Reasons for SVR₁₂ Non-Response

Subjects who do not achieve SVR₁₂ (SVR₁₂ non-responders) will be categorized as having:

1. On-treatment virologic failure (see **On-treatment virologic failure** definition);
2. Relapse (defined according to the **Relapse₁₂** definition for subjects who complete treatment);
3. Prematurely discontinued study drug with no on-treatment virologic failure (defined as any SVR₁₂ non-responder who prematurely discontinued study drug (duration $<$ 77 days, $<$ 49 days, and $<$ 38 days for 12 week, 8 week, and 6 week treatment regimens) and did not meet the **On-treatment virologic failure definition**);

4. HCV re-infection (see definition described earlier);
5. Missing follow-up data in the SVR₁₂ window (defined as any subject who completed study drug without data in the SVR₁₂ window and not meeting the definitions of [1], [2], [3], or [4]);
6. Other (defined as any SVR₁₂ non-responder not meeting the definitions of [1] – [5], such as a subject with a single quantifiable value within the SVR₁₂ window followed by an undetectable value beyond the SVR₁₂ window).

Reasons for SVR₂₄ Non-Response

Subjects who do not achieve SVR₂₄ (SVR₂₄ non-responders) will be categorized as having:

1. On-treatment virologic failure (see **On-treatment virologic failure definition**);
2. Relapse (defined according to the **Relapse₁₂** definition for subjects who complete treatment);
3. Relapsed after achieving SVR₁₂ (see **Relapse₂₄**);

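### A breakthrough first seen at the last on-treatment sample can be coded as non-virologic if new HCV therapy starts before, or on the day of, the confirming sample

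*SAP*

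**What the plan says.** **Confirmation.** SAP 10.1 defines a confirmed on-treatment value as two consecutive quantifiable results, "either both during treatment or at the final treatment measurement and the next consecutive post-treatment measurement". For breakthrough, the only waiver is a single value "followed by lost to follow-up will be considered a breakthrough (i.e., will not require confirmation".

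**New HCV therapy.** SAP 6.3 says HCV RNA values "measured on or after the start date of the new HCV treatment will be excluded from analyses". No exception is made for a value that would confirm a breakthrough. It adds: "The subject will be considered a failure for summaries of viral response at all time points after the start of the new HCV treatment".

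**Relapse.** SAP 10.1 has a wider waiver here. If the last available post-treatment value is quantifiable, "then the subject will be considered a relapse (i.e., will not require confirmation", whatever ended the usable follow-up. Relapse12 itself, however, requires HCV RNA below LLOQ at the Final Treatment Visit.

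**Coding of SVR12 non-responders.** Reason 3 in SAP 10.1 is "Prematurely discontinued study drug with no on-treatment virologic failure". Reason 5 is a completer with no data in the SVR12 window, and reason 6 is everything else. SAP 5.1.1 removes non-virologic non-responders from mITT-GT-VF. SAP 10.7 builds the primary virologic failure (PVF) population from breakthrough, relapse and failure to suppress, and leaves non-PVF subjects out of Analysis 2, the comparison of SVR12 by baseline variant.

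**Conduct.** Protocol 5.4.1.1 states that "Subjects should remain on study drug treatment until the virologic failure has been confirmed". For a premature discontinuation (D/C) visit, Protocol 5.4.1 states that "this visit should occur within 2 days following their final dose of study drugs and prior to the initiation of any other anti-HCV therapy". Table 4 lists an HCV RNA sample at that visit.

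**The concern.** Each rule is sensible alone; the difficulty is how they combine. Confirmation of a late breakthrough may depend on a sample taken after study drug stops. If new HCV therapy has begun by then, SAP 6.3 discards that sample. The subject is still in the 48-week follow-up, and Protocol 5.5.1 continues resistance monitoring whether or not other treatment is taken, so loss to follow-up does not describe the situation and the waiver is not triggered.

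At stake are the secondary on-treatment virologic failure rate, the reason table for SVR12 non-response, the only sensitivity analysis named in SAP 10.5, and membership of the PVF population. Subjects with a rebound have a reason to start another therapy, so any miscoding runs one way: fewer virologic failures and a higher mITT-GT-VF SVR12.

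**Working it through.** **Step 1. Trace the coding.** Take a 12-week subject who is below LLOQ at Week 10 and at or above LLOQ at the Week 12 draw, and who starts new HCV therapy before the next sample (scheduled at Post-Treatment Week 2 in Protocol Table 5).

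| Definition (SAP 10.1) | Met? | Why |
|---|---|---|
| Breakthrough, confirmed | No | The second value is excluded by SAP 6.3 |
| Breakthrough, waiver | No | The subject is not lost to follow-up |
| Failure to suppress | No | There are earlier values below LLOQ |
| Relapse12 | No | The Final Treatment value is at or above LLOQ |
| Re-infection | No | It also requires a Final Treatment value below LLOQ |

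With at least 77 days of drug the subject becomes reason 5, or reason 6 if the excluded results are still regarded as data in the window. If the last on-treatment sample was instead a D/C visit with less than 77 days of drug, the subject is reason 3.

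**Step 2. The same-day route.** Suppose the first breakthrough value came from an earlier visit and the D/C-visit sample would confirm it. Protocol 5.4.1 recommends that visit on the day drug stops and places it before other therapy. If new therapy starts later that day, the SAP 6.3 cut-off includes the start date and deletes a sample that the protocol places before new therapy. One breakthrough value remains, and Step 1 applies.

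**Step 3. Reproduce the SAP's interval.** Wilson 95% limits, with z² = 3.8415:

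[p + z²/(2n) ± z·√(p(1−p)/n + z²/(4n²))] / (1 + z²/n)

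For 9/10: centre = (0.9 + 0.1921)/1.3842 = 0.789; half-width = 1.960 × √(0.0090 + 0.0096)/1.3842 = 0.193. The limits are 59.6% and 98.2%, as in SAP 4.3. For 18/20 the formula gives 69.9% and 97.2%, also as stated.

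**Step 4. Size of one recoded subject.** Assumption: one affected subject per arm, with all others reaching SVR12. The documents give no expected count.

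| Arm size | Quantity | Coded virologic | As the SAP is written |
|---|---|---|---|
| 10 | On-treatment failure | 1/10 = 10.0% (1.8% to 40.4%) | 0/10 = 0% (0% to 27.8%) |
| 10 | mITT-GT-VF SVR12 | 9/10 = 90.0% (59.6% to 98.2%) | 9/9 = 100% (70.1% to 100%) |
| 10 | ITT SVR12 | 9/10 | 9/10 |
| 20 | On-treatment failure | 1/20 = 5.0% (0.9% to 23.6%) | 0/20 = 0% (0% to 16.1%) |
| 20 | mITT-GT-VF SVR12 | 19/20 = 95.0% (76.4% to 99.1%) | 19/19 = 100% (83.2% to 100%) |
| 20 | ITT SVR12 | 19/20 | 19/20 |

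Quick checks: the upper limit for 0/10 is 3.8415/13.8415 = 27.8%, and the lower limit for 9/9 is 9/12.8415 = 70.1%.

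**The case against.** A reader might infer that any virologic failure who moves to new HCV therapy is miscoded. The documents do not support that. Subjects are to stay on drug until failure is confirmed, and the D/C visit carries an HCV RNA sample and is to precede other therapy. SAP 6.1.2 counts a sample up to Study Drug End Day 2 as on-treatment. A breakthrough first seen at an earlier visit will therefore normally have two values before the cut-off. The same holds for a subject who stops on learning an open-label result: the D/C-visit sample supplies the second value unless new therapy starts that day. Failure to suppress needs no confirming value.

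A reader might also infer that resistance data are lost. SAP 10.7 still sequences non-PVF subjects without SVR12 who have a sample of at least 1000 IU/mL after discontinuation, and Analysis 3 lists their variants. What is lost is a place in the PVF-only listings and in Analysis 2.

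These limits stand, but they do not close the gap. Confirming before stopping cannot help when the first rebound appears at the scheduled end-of-treatment draw, so no protocol deviation is needed. Protocol 5.4.1 adds that D/C procedures should not hold up new treatment that the investigator considers necessary. In the 8- and 6-week arms, SAP Tables 3 and 4 have no visit window between Week 4 and the end of treatment, so a late rebound at scheduled visits would first appear at the final draw.

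**Conclusion.** The concern holds in a narrow form. When the first breakthrough value is the last on-treatment sample and new HCV therapy starts before the next sample, or when new therapy starts on the day of the confirming sample, the SAP as written can code a virologic failure as reason 3, 5 or 6. On-treatment failure is then understated, mITT-GT-VF SVR12 is overstated, and the subject leaves the PVF population and Analysis 2.

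It would be wrong to read this as a threat to the primary result. SAP 6.3 makes the subject a failure for viral response after new therapy starts, so ITT SVR12 is the same under either coding. No hypothesis test is attached to on-treatment failure.

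Frequency is low and may be zero; one subject per arm is only an illustration. In arms of 10, though, one subject is 10 percentage points. The protocol supplied covers Arms A and B only, so applying its safeguards to Arms C to F is an assumption.

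**What to change.** **SAP 10.1.** State that a single breakthrough value counts as breakthrough without confirmation when it is the last available value before loss to follow-up or before exclusion at the start of new HCV therapy. This parallels the relapse rule and covers both routes.

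**SAP 6.3, optional.** Keep a sample drawn on the start date of new HCV therapy when it is the D/C-visit sample, since Protocol 5.4.1 places that visit before new therapy. This keeps a real second value, whether or not it confirms. Do not make the rule depend on clock times of the first new dose: Protocol 5.2.3 specifies dates of administration and does not say that times are recorded.

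**Cost.** One or two sentences and a date comparison in programming, with no new data. The downside is that an isolated, unconfirmed value just before new therapy would count as virologic failure. That subject is already an SVR12 non-responder, so only the reason changes. The wording should be settled before the data are classified, because the study is open-label.

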10.7 Resistance Analyses

If possible, subjects treated with study drug during the Treatment Period who experience virologic failure will have resistance testing conducted if 1) they have on-treatment

breakthrough; 2) if they have post-treatment relapse (irrespective of the time of relapse), with a study drug duration \geq 77 days, 49 days and 38 days for 12-week, 8-week, and 6-week of treatment, respectively; or 3) if they have at least 6 weeks of treatment and fail to suppress by Week 6 (i.e., meet virologic stopping criteria). Subjects meeting one of these criteria will be referred to as subjects in the primary virologic failure (PVF) population, and a listing by subject that includes HCV subtype, IL28B genotype, reason for non-response, time point(s) sequenced as closest to time of VF, and HCV RNA value at the VF time point(s) will be produced for these subjects. In addition, all listings described below will display HCV subtype and reason for non-response in the subject identifier for each subject. A separate listing will delineate all subjects in the PVF population for whom no sequencing was performed (e.g., lost to follow-up while HCV RNA \leq 1000 IU/mL). Subjects treated with study drugs who do not achieve SVR₁₂ who do not meet the above criteria for the PVF population (e.g., those with less than 6 weeks of therapy who failed to suppress), but have a time point with HCV RNA \geq 1000 IU/mL after treatment discontinuation, will have the sample at that time point sequenced.

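### A lone final positive sample shown to be a new virus is counted as a relapse, because the SAP waives confirmation for relapse but not for re-infection

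*SAP*

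**What the plan says.** All the relevant rules are in SAP 10.1 unless stated otherwise.

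- **Confirmation.** After treatment, "a confirmed quantifiable post-treatment value is defined as two consecutive post-treatment HCV RNA measurements" at or above LLOQ.
- **Relapse.** Relapse12 applies to a subject with HCV RNA below LLOQ at the Final Treatment Visit "who completes treatment, excluding re-infection as described below". It ordinarily needs a confirmed value. But if the last available post-treatment value is at or above LLOQ, "then the subject will be considered a relapse (i.e., will not require confirmation").
- **Re-infection.** "HCV re-infection is defined as confirmed HCV RNA" at or above LLOQ after the end of treatment, "along with the post-treatment detection of a different HCV genotype, subtype, or clade compared with baseline". If phylogenetic analysis is technically impossible, a LiPA or Sanger result may stand in for it. That fallback does not relax the RNA condition.
- **New HCV therapy (SAP 6.3).** HCV RNA values "measured on or after the start date of the new HCV treatment will be excluded from analyses".
- **Sequencing (SAP 10.7).** Completers are tested "if they have post-treatment relapse (irrespective of the time of relapse"), but only samples of at least 1000 IU/mL are sequenced.
- **Reasons for SVR12 non-response.** Category 2 is relapse and category 4 is re-infection. Category 3, "Prematurely discontinued study drug with no on-treatment virologic failure", takes any such non-responder below the duration limit and does not exclude re-infection.
- **Reasons for SVR24 non-response.** Category 4 is the parallel entry. It excludes on-treatment failure, Relapse12 and Relapse24 but not re-infection, and its duration limit is 154 days.

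**The concern.** The two outcomes compete for the same subject but carry different evidence rules. Breakthrough and relapse can each be declared on one value when nothing follows it; re-infection cannot. The relapse exclusion removes only subjects who meet the stricter re-infection definition. Someone who misses that definition solely for want of a second RNA value falls back into relapse, even when the sequence evidence points to a new virus.

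Relapse is read as failure of the regimen, and Relapse12 is a secondary endpoint. With 10 or 20 subjects per arm, one misassigned subject is visible in the table. Correcting the label after the data are seen would be a departure from the SAP.

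**Working it through.** **1. The plan's own precision figure.** SAP 4.3 gives Wilson 95% intervals at 90% observed response. With z = 1.96, centre = (p + z²/2n)/(1 + z²/n) and half-width = [z/(1 + z²/n)]·√(p(1−p)/n + z²/4n²):

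- 9/10: centre 0.789, half-width 0.193, giving 59.6% to 98.2%.
- 18/20: 69.9% to 97.2%.

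Both match the SAP. They are not in dispute, and the same formula is used below.

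**2. The rules applied to post-treatment patterns.** Take a treatment completer with HCV RNA below LLOQ at the Final Treatment Visit. Here − is below LLOQ and + is at or above it.

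| Pattern | Virus | SAP as written | Last-value rule for both outcomes |
|---|---|---|---|
| − − − + (last) | new | relapse | re-infection |
| − − − + (last) | same | relapse | relapse |
| − − + + | new | re-infection | re-infection |
| − − + + | same | relapse | relapse |
| − − + − | either | neither | neither |

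Only the first row changes.

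**3. When the first row can occur.** There must be no second usable value. This happens on:

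- loss to follow-up after one positive;
- new HCV therapy before a retest, because SAP 6.3 then discards later values;
- an interim data cut (SAP 4.4.1) before a retest;
- a first positive at Post-Treatment Week 48, the last scheduled visit, with no retest.

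The virus must also be typed, which needs at least 1000 IU/mL for sequencing under SAP 10.7, or the LiPA/Sanger fallback.

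**4. Which results move.** The SVR12 window in SAP Table 5 is days 57 to 126 after the last dose.

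- *Positive by the SVR12 time point.* Relapse12, the reason for non-response, mITT-GT-VF and the primary virologic failure (PVF) population of SAP 10.7 are affected.
- *First positive at Week 48.* Only late relapse, overall relapse and the PVF population are affected.
- *ITT SVR12.* It is unchanged, because the subject's SVR12 status does not depend on the relapse or re-infection label.

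**5. Effect of one subject**, assuming all 10 or 20 are completers who stay in the denominator and, for mITT-GT-VF, that all others respond:

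| Measure | SAP as written | If classed as re-infection |
|---|---|---|
| Relapse12, n = 10 | 1/10 = 10.0% (1.8 to 40.4%) | 0/10 = 0% (0 to 27.8%) |
| Relapse12, n = 20 | 1/20 = 5.0% (0.9 to 23.6%) | 0/20 = 0% (0 to 16.1%) |
| mITT-GT-VF SVR12, n = 10 | 9/10 = 90.0% (59.6 to 98.2%) | 9/9 = 100% (70.1 to 100%) |
| mITT-GT-VF SVR12, n = 20 | 19/20 = 95.0% (76.4 to 99.1%) | 19/19 = 100% (83.2 to 100%) |

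**6. Frequency.** The documents give no re-infection rate, so 1 to 10 per 100 person-years is assumed. Exposure in the Relapse12 period, for 70 subjects over 84 to 126 days:

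- 70 × 84/365.25 = 16.1 person-years; 70 × 126/365.25 = 24.1 person-years.
- Lowest: 16.1 × 0.01 = 0.16. Highest: 24.1 × 0.10 = 2.4.

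That is about 0.2 to 2.4 re-infections of any kind. Only those with no second usable value are misclassified.

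**7. The reason lists.** A re-infected subject who stopped early without on-treatment failure meets SVR12 categories 3 and 4 together, and no precedence is stated. For SVR24, the longest regimen is 12 weeks, or 12 × 7 = 84 days. Essentially every subject is therefore under the 154-day limit, and a re-infected SVR24 non-responder who completed treatment also fits premature discontinuation.

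**The case against.** The best defence is that the asymmetry is conservative: removing a failure should need stronger evidence than counting one, and a single unconfirmed sample with a different sequence is weaker than two. Protocol 5.4.1.1 also asks for a post-treatment positive to be confirmed as soon as possible, so a second sample should usually exist. A subject positive by Post-Treatment Week 12 still has scheduled HCV RNA at Weeks 24, 36 and 48. A last value of 25 to 999 IU/mL would not be sequenced under SAP 10.7.

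Most of this stands as a limit on frequency. It does not remove the misclassification, because the SAP neither states a conservative intent nor says what happens when sequencing contradicts the relapse label. One might suppose that the relapse exclusion silently carries the last-value waiver, but the text does not say so.

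A reader might also infer that Week 48 re-infections distort the secondary endpoint or mITT-GT-VF. They do not: Relapse12 ends at the SVR12 time point, and a subject first positive at Week 48 has normally achieved SVR12 and stays in mITT-GT-VF as a responder. Nor is the full 48 weeks (70 × 336/365.25 = 64.4 person-years, or 0.6 to 6.4 re-infections at the assumed rates) the right exposure for Relapse12.

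**Conclusion.** The point holds in a limited form. On a literal reading of SAP 10.1, a lone final positive shown to be a different virus is a relapse. One such subject adds 10 percentage points to Relapse12 in a 10-completer arm, or 5 in a 20-completer arm, if the value falls by the SVR12 time point.

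A reader might infer that the primary result is at risk; it is not, since ITT SVR12 is the same either way. The case should be rare. The frequency range rests on an assumed re-infection rate, and the prompt-retest rule comes from a protocol text that describes only Arms A and B, so its application to Arms C to F is also assumed.

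The overlap in the reason lists is a separate wording fault with the same remedy. The 154-day limit must be corrected with it, or the SVR24 edit will be incomplete. This should be settled before database lock but does not threaten the study's main conclusion.

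**What to change.** In SAP 10.1:

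1. Define the RNA condition for re-infection as confirmed HCV RNA ≥ LLOQ, or a last available post-treatment value ≥ LLOQ, keeping the requirement for a different virus.
2. State that re-infection takes precedence over the last-value rule for relapse.
3. Footnote every re-infection accepted on a single RNA value.
4. Add *and not HCV re-infection* to SVR12 category 3 and SVR24 category 4.
5. In SVR24 category 4, replace the 154-day limit with those already in SVR12 category 3: under 77, 49 and 38 days for the 12-, 8- and 6-week regimens. The overall-relapse definition in the same section counts 37 days as completion for 6 weeks, so settle on one figure.

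Items 4 and 5 remove the re-infection overlap only. They do not make every pair of categories mutually exclusive; on-treatment failure and relapse, for example, still carry no mutual exclusion.

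The cost is a few words, with no new samples or assays. The downside is that the relapse count can only fall or stay the same, which is why the footnote matters.
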